Hypothesis 2: 150mg, 300mg, and 450mg L-DOPA will increase processing and gait speed, with greatest improvement occurring at the 450mg dosage level.

Exploratory aims: To obtain information on the dosing and tolerability of L-DOPA in our patient population as well as identify PET and MRI biomarkers associated with slowing.

Description of Subject Population

Sample #1

Specify subject population

adults aged >59 years with a depressive disorder, decreased processing speed, and decreased gait speed Number of completers required to accomplish study aims

48

Projected number of subjects who will be enrolled to obtain required number of completers

Age range of subject population 60 years or older

Gender, Racial and Ethnic Breakdown

On the basis of previous depression studies conducted in the Adult and Late Life Depression Research Clinic, it is anticipated that the sample will be composed of 60% women and 40% men as well as approximately 75% Caucasian, 15% African American, and 10% Hispanic subjects.

On the basis of previous depression studies conducted in the Adult and Late Life Depression Research Clinic, it is anticipated that the sample will be composed of 60% women and 40% men. Description of subject population

This phase will enroll 60 outpatients who (1) are aged \geq 60 years, (2) diagnosed with Diagnostic and Statistical Manual (DSM) 5 (107) MDD, Dysthymia, or Depression Not Otherwise Specified (NOS), (3) have Center for Epidemiologic Studies-Depression Rating scale (CES-D) (108) score \geq 10, (4) have decreased gait speed (defined as average walking speed over 15' course \leq 1m/s), and (5) are willing to and capable of providing informed consent and complying with study procedures.

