- 3. Next, processing speed will be assessed using Digit Symbol test from the WAIS-III, the Trail Making Test Part A, the Pattern Comparison Test, and the Letter Comparison Test. Previous research established that these tests were all reliable and valid (moderate to high loadings on the latent speed factor). Digit Symbol or Trails A will be used as a selection criterion, with patients included in this study if they scored 0.5 SD below the age-adjusted norms on Digit Symbol or Trails A. A latent factor (and subsequent factor score) will be extracted from the 3-test battery pre- and post-treatment and used as the main outcome in this pilot study. By extracting a latent factor and factor loadings we will utilize a more pure measure of processing speed for pre- post-testing than if we used the raw scores from an individual test or a sum total score from the three raw scores combined.
- 4. Patients' gait will be assessed as walking speed in m/s on a 15' walking course. Patients are instructed to walk at their usual or normal speed for a total of 27' (starting and ending at a point 6 feet prior to and after the 15' course to eliminate acceleration and deceleration effects). Two trials will be completed, and gait speed will be based on the average of 2 trials. Gait speed will be used as a selection criterion, with patients included in this study if they have a gait speed < 1 m/s.

5. Subjects will return the following week to review the results of the above testing. If subjects continue to be eligible for the study after review of their processing speed and gait speed, they will continue as below. Subjects who do not meet selection criteria after processing and gait speed measurement will be referred out.

MRI Scanning

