- 16. Drs. [name] and [name] continue to be Co-Investigators responsible for neuroimaging as part of a subcontract executed between RFMH and SUNY-Stony Brook. They will lead analyses of neuroimaging data. In terms of on-site execution of PET and MRI scans, these are supervised by the study PI ([name]) and/or [name], who works with the Aging Program as a study clinician and has a research background in PET neuroimaging.

Clinical treatment

- 16. An effort will be made for all subjects to be titrated up to 450mg L-DOPA over a 3 week-duration study. We chose 450mg as the target dose because it is higher than doses known to affect cognition (i.e., 150-300mg) but lower than levels used for PD (i.e., 600-1200mg) that may have greater side effects. Each subject will start taking 37.5mg carbidopa/150 mg levodopa (1.5 25/100 sinemet tablets) once daily for one week, then increase to 75mg carbidopa/300mg levodopa (1.5 25/100 sinemet tablets twice daily) for one week, and finally increase to 112.5mg carbidopa/450mg levodopa (1.5 25/100 sinemet tablets three times daily) for one week. Each subject will be titrated to 450mg L-DOPA unless they cannot tolerate higher doses, in which case subjects will have their dosage reduced to the maximum tolerable dose.
- 17. Although each subject is titrated up to 450mg L-DOPA if it is tolerated, the study design allows us to assess the effects and tolerability of three different L-DOPA doses (150mg, 300mg, and 450mg). Based on published work using L-DOPA for PD, we expect effects on cognition and gait to be apparent at each dosing level approximately 5 days after dosage increases. By performing assessments weekly, we will thus obtain measures of L-DOPA's effect on processing and gait speed at each dosing level. We carefully reviewed the literature and consulted our Co-Investigator [name] (neurologist and PD expert) for evidence of carry-over effects of L-DOPA dosing (such that prior experience with 150mg and 300mg may influence a subject's experience of receiving 450mg). We found little evidence to suggest there are significant carry-over effects from previous L-DOPA doses, so each dose will be able to be assessed on its own merits. Similarly, we do not anticipate that the repeated assessments of processing and gait speeds will bias the study results.

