- 18. In selecting L-DOPA doses, we balanced appropriate safety concerns regarding the use of this medication in a novel patient population with the goal of causing a measurable effect. L-DOPA is an extremely well tolerated medication at doses < 600mg, which is substantially less than the doses often reached in the treatment of Parkinson's disease (900-1200mg). L-DOPA has been administered to healthy subjects in single dose studies and found to be well-tolerated. In Parkinson's disease, a recent clinical trial published in the New England Journal of Medicine randomized patients to receive 150mg, 300mg, or 600mg L-DOPA for 40 weeks. In the 150mg and 300mg L-DOPA treatment groups, the only side effects

observed that were different from placebo were headache and nausea. No dyskinesias or other neuropsychiatric effects were observed that were greater than the placebo group. In terms of effects, single-dose studies have reported significant effects on cognition and neural activation with L-DOPA doses as low as 100mg. Thus, we believe the 150-450mg dose range to be used in this study will be both safe and likely to produce an observable effect.

Assessments

- 19. Subjects are expected to have a screening/evaluation visit, PET/MRI scanning day (for those receiving imaging), and weekly visits from Week 0-3.
- 20. At baseline, we will record each subject's chief complaint, referral source, age of onset of mood and/or cognitive decline, number prior depressive episodes, age, sex, marital status, race and ethnicity, years of education, employment status and income, years of education, family history. We also will document medical history, physical exam, urine drug screen, CBC, chemistries and electrolytes, thyroid profile, vitamin B12 and folate levels, urine analysis, and ECG. Vital signs will be measured at baseline and monitored weekly throughout the study. The Cumulative Illness Rating Scale-Geriatric (CIRS-G) (112) will be filled out at baseline to measure chronic medical illness burden. Subjects' current physical pain will be assessed weekly using a 100mm Pain Visual Analog Scale (VAS) and used as a covariate in analyses of gait speed (113).

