- 21. The following measures will be collected weekly throughout the study: 24-item HRSD, CGI Severity and Improvement, Structured Pill Count Interview, Unified Parkinson's Disease Rating Scale (UPDRS) (questions 32 and 33 will be used in this study to assess the duration and disability of dyskinesias caused by L-DOPA), Treatment Emergent Side Effect Scale, and Inventory of Depressive Symptoms—Self Report (IDS-SR).
- 22. In addition, processing and gait speed assessments will be performed weekly at 1pm to control for time of day effects and the duration since the last morning L-DOPA dose (anticipated to be 4 hours). Processing speed will be assessed using the Digit Symbol test from the Wechsler Adult Intelligence Scale-III (WAIS-III) (119) and the Pattern and Letter Comparison tests (120). These tests are all reliable and valid, with moderate to high loadings on the latent speed factor. A latent factor (and subsequent factor score) will be extracted from the 3-test battery pre- and post-treatment and used as the main outcome in the R61. By extracting a latent factor and factor loadings we will utilize a more pure measure of processing speed than if we used the raw scores from an individual test or a sum total score from the three raw scores combined (121-124).
- 23. Gait will be assessed as both a single and dual task (ST, DT) on a 15' walking course in the LLDC. For the ST, patients are instructed to walk at their usual or normal speed over the 15' walking course. For the DT, patients are instructed to walk at their usual pace while simultaneously verbally listing as many animals as possible (fluency DT). In addition, a counting DT will be used in which patients are instructed to walk at their usual pace while simultaneously performing serial subtractions by threes starting at 100 (125). Patients will start and end at a point 2 meters from beginning of the 15' course to eliminate acceleration and deceleration effects. Each ST and DT will be assessed two times with the average used in the analyses. The ST assessment of walking speed in m/s will be used as the primary outcome measure for this study.

End of study procedures

24. Following the 3 week duration treatment study, endpoint assessments will be made. Patients will enter 3 month open treatment period provided free of charge as described below.

You can upload charts or diagrams if any

Criteria for Early Discontinuation

Criteria for Early Discontinuation

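### In R61 the planned dose is exactly 150 mg times week, so neither the dose ranking in Hypothesis 2 nor a dose-dependent effect can be concluded; the weekly gradient is descriptive only

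*Combined protocol and SAP*

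**What the plan says.** Clinical treatment, item 16 (the dosing item), puts every subject on one ascending schedule: 150 mg/day for a week, then 300, then 450. The only departure is for subjects who cannot tolerate a step, "in which case subjects will have their dosage reduced to the maximum tolerable dose".

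Assessments, item 19, sets "weekly visits from Week 0-3", and item 22 says "processing and gait speed assessments will be performed weekly at 1pm".

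Item 17 reports little evidence of drug carry-over and infers from it: "so each dose will be able to be assessed on its own merits". The next sentence reads: "Similarly, we do not anticipate that the repeated assessments of processing and gait speeds will bias the study results".

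Hypothesis 2 (Specific Aims and Hypotheses) predicts improvement at all three doses, "with greatest improvement occurring at the 450mg dosage level".

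Speed and gait are also measured once off drug at screening (Evaluation, items 3 and 4): "Next, processing speed will be assessed using Digit Symbol test from the WAIS-III", and "Gait speed will be used as a selection criterion". Digit Symbol or Trails A is likewise used for selection.

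R61 describes no placebo arm, parallel dose arm, randomised order or washout; placebo comes in R33. The Statistical Analysis plan names chi-square and independent samples t-tests for dose-dependent increases, with no term for time. Summary of Experiences to Date already describes the increases as dose dependent.

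**The concern.** When all subjects climb the same dose ladder in step with the calendar, anything that improves with week or test number yields the same ordering as a dose response. Practice on timed tests, familiarity with the walking course and open-label expectation can all do this.

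Low carry-over does not help. It concerns whether last week's drug affects this week's score, not whether last week's test does. Testing at 1pm controls time of day, not test number.

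At stake is what R61 may claim about its main outcomes, the speed factor score and single-task gait. A reader will take dose dependence to mean that higher doses worked better. PET cannot fill the gap, because it uses a single 300 mg test dose and so cannot rank doses.

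**Working it through.** **1. The schedule.** Item 16 gives 1.5 tablets of 100 mg levodopa once, twice and three times daily: 1.5 × 100 × (1, 2, 3) = 150, 300, 450 mg, as stated. Week 0 is taken as 0 mg (before treatment). Dose at Weeks 0–3 is then 0, 150, 300, 450 = 150 × week.

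**2. Identifiability.** The design matrix [1, week, dose] has rank 2 of 3. Only the sum of the weekly time effect and the drug effect per 150 mg can be estimated. The reported effect size at 450 mg for processing speed is 0.41. If linear, the sum is 0.41/3 = 0.137 SD per step, and the drug effect at 450 mg is 0.41 − 3 × (practice per week):

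| Assumed practice per week (SD) | Drug effect left at 450 mg (SD) |
|---|---|
| 0 | 0.41 |
| 0.05 | 0.26 |
| 0.10 | 0.11 |
| 0.137 | 0.00 |

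A drug effect of 0.20 SD at every dose, plus 0.07 SD per week of practice, gives 0.27, 0.34 and 0.41. That looks like a gradient, but the drug effect has none.

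**3. Does the screening test break the tie?** Count sessions 0–4 and dose in 150 mg units: 0, 0, 1, 2, 3. Sums of squares are 10 and 6.8, and the cross-product is 8. Correlation = 8/√(10 × 6.8) = 0.97. VIF = 1/(1 − 64/68) = 17, so the dose-slope SE is √17 = 4.1 times larger once a practice term is included. Even this needs practice to be a straight line and no rebound after selection on the screening values.

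**4. Illustration of size.** The documents give no practice effect, so drift is assumed and the drug effect is set to zero. Test: paired Week 3 minus Week 1, two-sided 5%, n = 36, compound symmetry with between-visit correlation r. The change has variance 2(1 − r), and power comes from the noncentral t with noncentrality drift × √n / √(2(1 − r)). Example at r = 0.79 and 0.10 SD per session: 0.20 × 6/√0.42 = 1.85, giving 43.7%.

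| Drift | Week 3 − Week 1 (SD) | Paired test, r = 0.70 to 0.85 |
|---|---|---|
| None | 0 | 5% |
| Gains at Weeks 1–3 of 0.07, 0.035, 0.0175 SD (largest gain before Week 0) | 0.0525 | 7–9% |
| Gains at Weeks 1–3 of 0.14, 0.07, 0.035 SD | 0.105 | 12–20% |
| 0.05 SD per session | 0.10 | 12–19% |
| 0.10 SD per session | 0.20 | 32.5–57% |
| 0.14 SD per session | 0.28 | 56–85% |

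The last row is an extreme: 3 × 0.14 = 0.42 SD, so practice would account for the whole observed 0.41 SD.

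**5. Which test?** The paired test is an assumption; the SAP names independent samples t-tests. Simulating that test on the same data (40,000 trials per setting) gives under 9% in every row, because it ignores the within-person correlation. But the reported p-values do not fit it. With two sets of 36, t = 0.41 × √18 = 1.74 and p is about 0.09; with 33 (after the 8.3% drop-out, 3 of 36), p is about 0.10. The reported p is 0.001.

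**6. Where r comes from.** If the analysis was paired and the effect size is in baseline SD (both assumed), the SD of change is ES × √n / t and r = 1 − (SD of change)²/2. Processing speed: 0.41 × 6/3.591 = 0.685, so r = 0.77 (0.79 with n = 33). Dual-task gait (0.43, p = 0.003): r = 0.67 (0.70 with n = 33), so gait sits near the lower ends of the ranges.

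**The case against.** - **The rates depend on a test the SAP does not name.** This stands as a limit on the size. Under the named test a false trend is rare in these settings. The aliasing does not depend on the test, and the reported p-values fit a paired analysis.
- **Practice may be small, or mostly spent before Week 0.** It may. The decelerating scenarios give only 7–20%. Nothing in the documents settles which row applies.
- **Dose reductions and the screening test break the identity.** Reductions follow intolerance and are not random. The screening test helps only under the conditions in step 3. The biases found for that adjusted slope (practice gains that halve each session, or selection rebound) run against a dose effect, so reporting the screening-to-Week-0 change descriptively is reasonable.
- **R61 is a pilot, and R33 is placebo-controlled.** True, and dosing information is listed as exploratory. For processing speed, item 22 defines the main outcome as a factor score before and after treatment, not a weekly gradient. But the ranking is part of Hypothesis 2 under Aim 2, outside the exploratory aims, and dose dependence has already been reported.

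A reader might infer that L-DOPA had no effect, that the gradient is an artefact, or that a wrong dose goes forward to R33. The documents support none of these. A design that cannot separate dose from time cannot show the drug effect to be absent, and no passage says that the weekly gradient selects the R33 dose.

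**Conclusion.** The concern holds. Over Weeks 0–3 planned dose is an exact multiple of week, so the R61 data cannot rank the three doses or establish dose dependence. This follows from the schedule alone. The inference that each dose can be judged separately does not follow from low carry-over, and the statement about repeated assessments is unsupported.

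The size of the distortion is not established. The illustrative rates rest on assumed drift, an assumed between-visit correlation of 0.70–0.85 and an assumed paired test. They are not the trial's error rate.

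The same limit applies to any on-drug visit compared with Week 0: it is an uncontrolled pre-post change, so the progress summary's statement that L-DOPA improved processing and gait speed is also stronger than the design allows.

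**What to change.** - **Clinical treatment, item 17.** Keep the carry-over statement. Remove the inference that each dose can be assessed separately. Replace the repeated-assessment sentence with a statement that dose level is confounded with week, practice and time.
- **SAP and any report.** Present the dose gradient and the ranking part of Hypothesis 2 as descriptive only. Replace the dose-dependence wording with *increases over the three weeks of titration*. State that the weekly gradient alone is not evidence of which dose engages the target best.
- **Baseline.** State that the Week 0 to on-drug change is an uncontrolled pre-post change with the same limit, and name Week 0, not the screening value used for selection, as its baseline. Item 22 does not say which pre-treatment value is meant.
- **Dose carried to R33.** The Lay Summary names the best-tolerated dose; Specific Aims and Hypotheses names the dose with optimal target engagement. These must be reconciled; no dose or rule is proposed here.

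Cost: wording and a named baseline. Interventions are complete and only analysis is ongoing, so no new data or model is needed. The price is a weaker R61 conclusion on dose ranking.

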I am submitting an annual continuation without modifications

Division & Personnel

Division

What Division/Department does the PI belong to?

Psychiatry

Within the division/department, what Center or group are you affiliated with, if any? program on healthy aging and late life brain disorders

Unaffiliated Personnel

List investigators, if any, who will be participating in this protocol but are not affiliated with New York State Psychiatric Institute or Columbia University. Provide: Full Name, Degrees and Affiliation.

[name] (SUNY Stony Brook)

[name] (SUNY Stony Brook)

Application for Continuation of Research

Status

Current Status of Study:

All research interventions were completed. Only data analysis is ongoing.

Summary of Experiences to Date

Please provide a summary of scientific progress of the study and the experience of research participants, to date. This requirement is designed to allow for the investigator and the IRB to reassess the study's risks and benefits in terms of developments in the field, changing practice patterns, and new IRB policies and procedures.

36 subjects participated who were 75.3 ± 7.5 years old and 44.4% male. Significant, dose dependent increases in processing and gait speed were observed with L-DOPA (450mg dose: processing speed factor score effect size [ES] = 0.41, p = 0.001; dual task gait speed ES = 0.43, p = 0.003). [11C]raclopride Δ BPND was significantly different from 0 in sensorimotor (t = -4.85, df = 24, p < 0.001) and associative striatum (t = -2.52, df 24, p = 0.019) but not in limbic striatum (t = 0.265, df = 24, p = 0.793). Depressive symptoms decreased significantly on the Hamilton Rating Scale for Depression (ES = -0.4, p = 0.01). Drop-out rate was 8.3%, and nausea was the most frequently-reported side effect. By enhancing availability of dopamine, L-DOPA improved processing and gait speed in depressed older adults and significantly decreased [11C]raclopride binding in selected striatal subregions.

Funding

Have there been any changes in funding status since the prior approval?

No

Have the principal investigator and other investigators made all required disclosures of financial interest in the study sponsor/product?

Yes

Summary

Have there been any study findings, recent literature, or untoward events occurring here or at other sites in the past year which might affect the analysis of the safety, risks or benefits of study participation? No

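### Item 17 expects no bias from repeated testing but offers evidence only on drug carry-over, so practice and L-DOPA effects on processing speed cannot be separated

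*Combined protocol and SAP*

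**What the plan says.** Evaluation, item 3, gives the "Digit Symbol test from the WAIS-III, the Trail Making Test Part A, the Pattern Comparison Test, and the Letter Comparison Test" before treatment. Item 5 adds: "Subjects will return the following week to review the results of the above testing". Assessments, item 19, lists an evaluation visit, a scan day for the imaged subset, and "weekly visits from Week 0-3". Item 22 states that "processing and gait speed assessments will be performed weekly at 1pm" and "Processing speed will be assessed using the Digit Symbol test from the Wechsler Adult Intelligence Scale-III", together with the Pattern and Letter Comparison tests. A factor score is "extracted from the 3-test battery pre- and post-treatment and used as the main outcome in the R61".

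Clinical treatment, items 16 and 17, titrate every subject upward through 150, 300 and 450 mg in successive weeks and read each week's score as the effect of that week's dose. Item 17 reports a literature search and an expert consultation on carry-over between doses, and then says: "Similarly, we do not anticipate that the repeated assessments of processing and gait speeds will bias the study results".

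The Statistical Analysis Plan names chi-square and independent-samples t-tests and nothing else for these outcomes. The Summary of Experiences to Date reports an effect size (ES) of 0.41 with p = 0.001 for the factor score at 450 mg and concludes that "L-DOPA improved processing and gait speed in depressed older adults".

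**The concern.** Scores on timed tests can rise with repetition as subjects learn the symbol key and the format. This phase has no arm tested on the same schedule without L-DOPA, so nothing in the design shows how much of a before-after gain is learning. Because dose and test occasion rise together, a cumulative practice gain would also be largest at 450 mg, the ordering that Hypothesis 2 predicts for the drug.

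Item 17 is the only place where the plan addresses this, and its evidence answers a different question. Whether an earlier dose alters the response to a later one says nothing about whether an earlier sitting alters a later score.

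At stake are the causal wording of the reported result, the reading of the dose gradient, and one of the conditions for moving to R33.

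**Working it through.** **1. Sittings and time span.** Evaluation plus Weeks 0, 1, 2 and 3 gives five sittings. This is the plain reading of items 3, 19 and 22 but is not stated as a count; it falls to four if the evaluation test doubles as Week 0. Item 5 puts the return visit about one week after evaluation. If that visit is Week 0, evaluation to Week 3 spans about four weeks; it is longer if scans or a separate visit intervene.

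**2. Which sittings count.** Item 22 does not say which test is the pre-treatment one. If it is Week 0, three retests follow it. If it is evaluation, four do. Practice gained before the pre-treatment test does not enter the change score; practice gained after it enters in full. Forming a factor score does not remove a gain shared by all three tests.

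**3. Can the reported result be reproduced?** Inputs from the Summary: 36 participants, 8.3% drop-out (3/36), so 33 completers; ES = 0.41; p = 0.001. The documents state no alpha, so two-sided 0.05 is assumed.

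- Independent-samples t-test, as named in the SAP: t = 0.41 × √(33/2) = 1.67, p = 0.10 (p = 0.086 with n = 36). No match.
- Paired, ES in units of the SD of change: t = 0.41 × √33 = 2.36, p = 0.025 (p = 0.019 with n = 36). No match.
- Paired, ES in baseline-SD units: p = 0.001 on 32 df needs t = 3.622, so SE = 0.41/3.622 = 0.113. With SE = √(2(1 − r)/n), this implies a pre-post correlation r = 1 − 33 × 0.113²/2 ≈ 0.79 (0.77 with n = 36). It matches only if r has about that value, which the documents do not give.

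**4. Break-even practice gain.** This is the total gain g at which ES − g is no longer significant: g = 0.41 − t(0.975, 32) × SE.

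- Baseline-SD reading: 0.41 − 2.037 × 0.113 = 0.18 SD (0.178 with n = 36).
- SD-of-change reading: SE = 1/√33 = 0.174, so 0.41 − 2.037 × 0.174 ≈ 0.055 SD. This reading does not reproduce p = 0.001.

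**5. Range, since the actual gain is unknown** (baseline-SD reading, n = 33, SE 0.113). The last column is the chance that a noncentral t on 32 df with noncentrality g/0.113 exceeds 2.037.

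| Assumed total practice gain g (SD) | ES − g | p | Chance of a significant gain with no drug effect |
|---|---|---|---|
| 0 | 0.41 | 0.001 | 2.5% |
| 0.10 | 0.31 | 0.010 | 13.5% |
| 0.20 | 0.21 | 0.073 | 40% |
| 0.30 | 0.11 | 0.34 | 73% |
| 0.41 | 0 | 1.0 | 94% |

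**The case against.** The strongest defence is that R61 is deliberately a single-arm first stage, with the placebo comparison reserved for R33, and that item 17 only states an expectation. Both are true. The staged design explains the missing control arm, but it does not support a causal statement from R61 or supply evidence that practice is nil.

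A second defence is that the evaluation sitting already acts as a practice exposure before Week 0. It may absorb part of the learning, and if learning slows with repetition, Weeks 1 to 3 would contribute less. This helps only if Week 0 is the pre-treatment score, which the plan does not say. It is also a reason not to divide the break-even gain evenly across retests.

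A third is that R33 does not hang on this score alone. That stands. A reader might infer that a practice effect by itself could trigger the go decision, but Specific Aims also requires increased dopamine release, and the PET measure does not depend on timed tests.

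Finally, item 23 calls single-task gait speed the primary outcome, while item 22 gives the factor score as the main one. The weight of this point depends on how the two items are reconciled.

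**Conclusion.** The concern holds as a matter of design. The expectation in item 17 is unsupported for practice, and neither the design nor the SAP separates practice from drug effect on the factor score. Any gain after the baseline test is counted with L-DOPA and can reproduce the predicted dose ordering.

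The size of the bias is unknown. A reader might infer that practice explains the whole 0.41, or that the reported result is false. The documents contain no practice estimate and support neither conclusion. The 0.18 SD break-even is an illustration resting on 33 completers, two-sided alpha 0.05, ES in baseline-SD units and a back-solved SE of 0.113. The reported ES and p do not agree under the test named in the SAP, so the figure should not be published as the trial's own. Confidence is high that the bias is uncontrolled and low on how large it is.

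**What to change.** **In the plan.** Withdraw the item 17 sentence. Define Week 0, not evaluation, as the pre-treatment score, so that the evaluation sitting serves as a practice exposure. Reconcile items 22 and 23 on which outcome is primary.

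**For any further use of this battery.** Use parallel forms of Pattern and Letter Comparison and re-paired Digit Symbol keys, with form order rotated across subjects. The cost is printing and administration. Forms may differ slightly in difficulty, which rotation balances across subjects, and learning of the test format is not fully removed.

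**For the completed data.** All interventions are finished, so only analysis and wording can change. Report that processing speed increased over repeated testing during open-label L-DOPA, and do not attribute the gain or its dose ordering to L-DOPA alone. State which sitting was used as baseline and what SD the ES is expressed in. Beside the ES, give the break-even practice gain, ES − t × SE, using the SE from the actual analysis. This needs no new data; the cost is a more cautious claim.
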